5.0 TREATMENT PROGRAM

5.1 Overview of Treatment Plan

A cycle of therapy is 29 days. Following the end of flotetuzumab infusion on Day 29, patients will be allowed a treatment free interval of up to 3 days to allow respite. The duration of this treatment free interval will be up to the treating physician's discretion. Keeping interruptions to \leq 3 days will reduce the chance of disease rebound and lower the risk for recurrent CRS based upon clinical experience in flotetuzumab-treated adult patients. Alternatively, the treating physician may opt to skip the treatment-free interval and allow the patient to proceed immediately to the next cycle without respite, as long as the patient is experiencing clinical benefit. Clinical benefit may be defined as a reduction in leukemia related symptoms, and/or a reduction in transfusion frequency and/or a reduction or clearance of peripheral blasts. Patients with at least a PR following Cycle 2 may continue on subsequent cycles of flotetuzumab for a total of up to 6 cycles, lasting approximately 6 months. Patients should discontinue protocol therapy if they have not achieved at least a PR following Cycle 2.

During the dose escalation portion of the study, flotetuzumab will be administered by continuous intravenous infusion for a total of 28 days (NOTE: infusion ends on Day 29).

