9.3 Useful Links and Contacts

- CTEP Forms, Templates, Documents:
<http://ctep.cancer.gov/forms/>
- NCI CTEP Investigator Registration:
[contact]
- CTEP Identity and Access Management (IAM) account:
<https://ctepcore.nci.nih.gov/iam/>
- CTEP Associate Registration and IAM account help:
[contact]
- IB Coordinator:
[contact]

10.0 CRITERIA FOR REMOVAL FROM PROTOCOL THERAPY AND OFF STUDY CRITERIA**10.1 Criteria for Removal from Protocol Therapy**

- a) Clinical (including physical examination or serum tumor markers) or radiographic

THIS PROTOCOL IS FOR RESEARCH PURPOSES ONLY, SEE PAGE 1 FOR USAGE POLICY

evidence of progressive disease (See [Section 12](#)).

- b) Have not achieved at least a PR following 2 successive treatment cycles.
- c) Adverse Events requiring removal from protocol therapy (See [Section 13](#)).
- d) Development of a DLT following 1 dose reduction.
- e) An infusion stop or delay of more than 2 weeks due to AE or more than 2 discontinuations per cycle due to AE (does not apply for prolongation of the scheduled treatment free period of a cycle).
- f) Refusal of protocol therapy by patient/parent/guardian
- g) Non-compliance that in the opinion of the investigator does not allow for ongoing participation.
- h) Completion of 6 cycles of therapy.
- i) Physician determines it is not in the patient's best interest.
- j) Repeated eligibility laboratory studies (CBC with differential, bilirubin, ALT (SGPT) or serum creatinine) are outside the parameters required for eligibility prior to the start of flotetuzumab (See [Section 8.1](#)).
- k) Study is terminated by Sponsor.
- l) Pregnancy

Patients who are removed from protocol therapy during Cycle 1 should continue to have the required observations in [Section 8.1](#) until the originally planned end of the cycle or until all adverse events have resolved per [Section 13.4.4](#), whichever happens LATER. The only exception is with documentation of the patient's withdrawal of consent. Patients who are removed from protocol therapy in subsequent cycles should have the necessary observations to ensure adequate clinical care.

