12.2 Response Criteria for Patients with Leukemia

Patients must have received ≥ 1 cycle of flotetuzumab, be evaluable for DLT, and have had ≥ 1 bone marrow evaluation(s) following treatment. Response will be defined as best response after up to 4 cycles. The AML response criteria are derived from the revised AML International Working Group (IWG) Criteria.³⁸ It is anticipated that patients who achieve morphologic remission with study treatment may proceed to subsequent allogeneic HSCT at the treating physician's discretion.

THIS PROTOCOL IS FOR RESEARCH PURPOSES ONLY, SEE PAGE 1 FOR USAGE POLICY

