12.2.4 Partial Response (PR)

A decrease of at least 50% in the percentage of blasts to 5% to 25% in the bone marrow aspirate. Bone marrow must have adequate cellularity (e.g., > 15%) to determine response. PR status will not be included in calculation of response to the regimen. A repeat bone marrow aspiration after several weeks may be required to distinguish between a PR and increased blasts caused by bone marrow regeneration. A value of < 5% blasts may also be considered a PR if Auer rods are present.

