- b. Physical exam (including VS). Prior to subsequent cycles.
- c. CBC/diff/platelets. Weekly. If patients develop Grade 4 neutropenia then CBCs should be checked at least every 3 to 4 days until recovery to Grade 3 or until meeting the criteria for dose limiting toxicity.
- d. Ht/Wt/BSA. Prior to subsequent cycles.
- e. Electrolytes including Ca⁺⁺. Prior to subsequent cycles.
- f. Creatinine, ALT, bilirubin, and AST. Prior to subsequent cycles.
- g. Albumin. Prior to subsequent cycles.
- h. Imaging (CT or MRI) of chloroma. Only to be performed if clinically indicated. At the end of every cycle (if present on previous study).
- i. ECHO or gated radionuclide study. Prior to subsequent cycles.
- j. EKG. Prior to subsequent cycles.
- k. Neurologic exam. Prior to subsequent cycles.
- l. CD3 T-lymphocyte quantification. In consenting patients, samples to be collected on Day 1 of Cycles 2+. See [Section 8.6](#) for details.
- m. Cytokine production measurement. If patients experience IRR/CRS, blood samples are to be collected from consenting patients at the time of IRR/CRS and at the time of IRR/CRS resolution (if applicable). See [Section 8.7](#) for details.
- n. Bone marrow aspirate. At the end of every cycle.
- o. Immunogenicity study. Samples to be collected from all patients on Cycle 3, Day 1 (pre-infusion), and on Cycle 5, Day 1 (pre-infusion). See [Section 8.3](#) for details.
- p. Pharmacokinetics. Blood samples will be collected 30 minutes, 1 hour, 2 hours, 4 hours, 8 hours, and 24 hours after the end of infusion on the patient's last day of

THIS PROTOCOL IS FOR RESEARCH PURPOSES ONLY, SEE PAGE 1 FOR USAGE POLICY

protocol therapy. See [Section 8.2](#) for details.

- q. NGS MRD comparison with flow cytometry MRD. In consenting patients only at the time of bone marrow evaluation. See [Section 8.5](#) for details.
- r. Flow cytometry with MRD determination. At the end of each cycle with bone marrow evaluation.

This listing only includes evaluations necessary to answer the primary and secondary aims. OBTAIN OTHER STUDIES AS REQUIRED FOR GOOD CLINICAL CARE.

Comments

(Include any held doses, or dose modifications)

THIS PROTOCOL IS FOR RESEARCH PURPOSES ONLY, SEE PAGE 1 FOR USAGE POLICY

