APPENDIX IX: NGS MRD COMPARISON WITH FLOW CYTOMETRY MRD STUDY FORM

COG Pt ID # _____ Cycle 1, Day 1 Date: _____

Please do not write patient names on this form or on samples.

Patient Weight: _____ kg

Flotetuzumab Dose Level: _____ nanograms/kg/day Flotetuzumab Total Daily Dose: _____ nanograms

Bone marrow samples (10 – 15 ml) will be collected from consenting patients at the time of each bone marrow evaluation.

Record the exact time the bone marrow sample is collected at the end of each cycle.

Bone Marrow Sample No.	Scheduled Collection Time	Actual Date Sample Collected	Actual Time Sample Collected (24-hr clock)
1	Prior to Cycle 1	/ /	____:____
2	At the end of Cycle 1	/ /	____:____
3	At the end of Cycle 2	/ /	____:____
4	At the end of Cycle 3	/ /	____:____
5	At the end of Cycle 4	/ /	____:____
6	At the end of Cycle 5	/ /	____:____
7	At the end of Cycle 6	/ /	____:____

One copy of this NGS MRD Comparison with Flow Cytometry MRD Study Form should be uploaded into RAVE. A second copy should be sent with the samples to the address listed in [Section 8.5.6](#). See [Section 8.5](#) for detailed guidelines for packaging and shipping NGS MRD Comparison with Flow Cytometry MRD samples.

Signature: _____ Date: _____
(site personnel who collected samples)

THIS PROTOCOL IS FOR RESEARCH PURPOSES ONLY, SEE PAGE 1 FOR USAGE POLICY

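### Best response is counted over at most 4 cycles while treatment and marrow evaluation can run to 6, so a first remission in Cycle 5 or 6 would be left out of the descriptive response rate

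*Combined protocol and SAP*

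**What the plan says.** Section 12.2 sets the window for the response endpoint: "Response will be defined as best response after up to 4 cycles". Section 12.2.4 adds that "PR status will not be included in calculation of response to the regimen".

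Treatment can last longer than that window. Section 5.1 says: "Patients with at least a PR following Cycle 2 may continue on subsequent cycles of flotetuzumab for a total of up to 6 cycles", and also: "Patients should discontinue protocol therapy if they have not achieved at least a PR following Cycle 2". The abstract and Sections 2.5 and 11.1 give the same 6-cycle maximum. Section 10.1 lists "Completion of 6 cycles of therapy" among the reasons for coming off protocol therapy.

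Marrow evaluation follows treatment. Appendix V requires: "Bone marrow aspirate. At the end of every cycle". The table in Section 8.1 agrees, and the NGS MRD form in Appendix IX has a last line reading "At the end of Cycle 6".

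No section explains the 4-cycle limit or says how a remission first seen in Cycle 5 or 6 is to be reported.

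**The concern.** A PR is enough to stay on treatment after Cycle 2 but does not count as response. Patients who continue in PR are the ones who could still convert to remission late, and the window closes two cycles before their treatment has to end. Section 12.2 also expects that patients in remission may leave for transplant. Those still on drug at Cycle 5 may therefore include a fair share who have not yet remitted.

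At stake is the activity read-out under secondary aim 1.2.2. A remission documented on study drug, at a marrow the protocol requires, would not enter the response rate. Other sections use remission status without the limit, so the same patient could be classified in two ways within one report.

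**Working it through.** **1. The plan's own figures.** No sample size is stated for response. The enrolment figures in Section 11.1 reproduce with 10% inflation:
- anticipated maximum: (18 + 6) / 0.9 = 26.7, rounded up to 27, as stated;
- absolute maximum: (3 × 12 + 6) / 0.9 = 42 / 0.9 = 46.7, rounded up to 47, as stated.

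Neither depends on response, so changing the response window leaves both as they are.

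**2. Treatment, marrow schedule and window side by side.** The last column is a constructed patient.

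| End of cycle | Treatment allowed (5.1) | Marrow required (8.1, App. V) | Inside 12.2 window | Example patient |
|---|---|---|---|---|
| 1 | yes | yes | yes | SD |
| 2 | yes | yes | yes | PR |
| 3 | yes, if PR or better after Cycle 2 | yes | yes | PR |
| 4 | same | yes | yes | PR |
| 5 | same | yes | no | CR |
| 6 | same | yes | no | CR |

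Best response inside the window is PR. Section 12.2.4 excludes PR, so this patient adds nothing to the numerator of the response rate despite a documented CR on protocol therapy. Over all six cycles the best response is CR, and the patient counts.

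**3. Direction.** Best response over six evaluations cannot be worse than over the first four of them. The 4-cycle rate is therefore equal to or below the 6-cycle rate.

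**4. Size per patient.** With k late first remissions among n response-evaluable patients, the rate changes by k/n. The documents give neither k nor n for response. The values of n below are illustrative, built from cohort sizes in Sections 11.1 and 11.2.2. The true n could be lower, because Section 12.2 also requires at least one cycle, DLT evaluability and a post-treatment marrow.

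| n | Origin | k = 0 | k = 1 |
|---|---|---|---|
| 6 | one cohort | 0 | 1/6 = 16.7 points |
| 12 | one expanded cohort | 0 | 1/12 = 8.3 points |
| 24 | 18 + 6 | 0 | 1/24 = 4.2 points |
| 42 | 36 + 6 | 0 | 1/42 = 2.4 points |

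For scale, Section 2.3.1 reports an adult CR/CRi rate of 5/27 = 18.5%. Near that rate, one added remission gives, with exact 95% intervals:
- n = 12: from 2/12 = 16.7% (2.1% to 48.4%) to 3/12 = 25.0% (5.5% to 57.2%);
- n = 24: from 4/24 = 16.7% (4.7% to 37.4%) to 5/24 = 20.8% (7.1% to 42.2%).

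The shift is visible in a reported percentage but lies well inside the uncertainty of the estimate.

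**5. Consistency across sections.** Sections 8.2.1 (PK) and 8.3.1 (immunogenicity) contrast patients who reach CR/CRi with those who do not. They state no cycle limit and do not refer to 12.2. Section 11.5 says that disease evaluations follow Section 8.1 and that response is described, again without a limit. Read literally, the example patient is CR/CRi in 8.2.1 and 8.3.1 and PR in 12.2.

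**The case against.** A fixed best-response window is an ordinary design choice, and the affected group is narrow. It needs a PR at Cycle 2, no remission through Cycle 4, no progression, treatment into Cycle 5 or 6, and then a first remission. Response is a secondary aim, described as preliminary. Section 11.5 calls these analyses descriptive and exploratory, and there is no target rate, futility rule or go/no-go decision on response. All of this stands, and it limits the point to a minor correction. It does not supply a reason for stopping at 4 cycles or a rule for later remissions.

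Four stronger readings are tempting, and the documents do not support them.

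- *Late remitters are placed in the comparator group of the PK, immunogenicity and biomarker comparisons.* Sections 8.2.1 and 8.3.1 have no cycle limit, so on their face they count such a patient as CR/CRi. The biomarker text in 8.4.1, 8.6.1 and 11.5 speaks of response, antitumor effect or outcome, and does not use CR/CRi grouping. What exists is an unresolved ambiguity between sections.
- *The patient is scored a non-responder and the remission is discarded.* The protocol has no non-responder category. The recorded category is PR, and Section 11.5 does not prevent a Cycle 5 or 6 remission from being described. Only the best-response classification, and the rate built on it, is cut off.
- *A third of the response information is lost.* Two of six end-of-cycle marrows fall outside the window, but that is a share of visits. It does not measure bias.
- *The trial's conclusion about a 6-cycle regimen would be wrong.* The protocol plans no formal conclusion on activity.

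**Conclusion.** The point holds in limited form. As written, 12.2 and 12.2.4 together leave a first CR, CRp or CRi in Cycle 5 or 6 out of the response rate for aim 1.2.2, although the treatment and the marrow that document it are both part of the protocol. The rate can only be lowered or left unchanged. Each affected patient is worth 1/n, and the total is unknown and may be zero.

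The primary DLT assessment, MTD/RP2D and the enrolment totals of 27 and 47 are not affected. The conclusion assumes that the 12.2 window applies literally to the response rate and that no unpublished rule covers later remissions.

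**What to change.** In Section 12.2, define best response as the best category documented at any disease evaluation of protocol therapy, up to 6 cycles. Name the repeat marrows allowed under 12.2.4 (to separate PR from regeneration) and 12.2.8 (hypocellular marrow) as included. Wording limited to scheduled evaluations, or to evaluations made while on drug, could drop these repeats, some of which may fall after the last cycle.

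List for each responder the cycle in which CR, CRp or CRi was first documented. If a 4-cycle figure is wanted, report best response through Cycle 4 as a secondary line. State in 8.2.1, 8.3.1 and 11.5 that the same remission definition and window apply. Settle this before response data are analyzed, so that the window is not chosen with results in view.

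The cost is a short wording amendment and one extra line of descriptive reporting. The end-of-cycle marrows are already required, and no procedure, patient or treatment rule changes.

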12.2.1 Complete Remission (CR)

Attainment of an M1 bone marrow (< 5% blasts) with no evidence of circulating blasts or extramedullary disease and with recovery of peripheral blood counts (ANC $\geq 1000/\text{mm}^3$ and platelet count $\geq 100,000/\text{mm}^3$). Occasionally, rare peripheral blood blasts may be identified during marrow regeneration; however, the marrow must be M1 status by morphology and without Auer rods to be considered CR. Flow cytometry may also be useful to distinguish between leukemia and a regenerating bone marrow. There is no requirement for bone marrow cellularity.

12.2.2 CR with Partial Recovery of Platelet Count (CRp)

Attainment of an M1 bone marrow (< 5% blasts), no evidence of circulating blasts or extramedullary disease, and recovery of ANC $\geq 1000/\text{mm}^3$ and platelet transfusion independence (defined as no platelet transfusions in 1 week).

12.2.3 CR with incomplete blood count recovery (CRI)

Attainment of an M1 bone marrow (< 5% blasts), no evidence of circulating blasts or extramedullary disease and with ANC $< 1000/\text{mm}^3$ or platelet count $< 100,000/\text{mm}^3$ without platelet transfusion independence (defined as no platelet transfusions in 1 week).

12.2.4 Partial Response (PR)

A decrease of at least 50% in the percentage of blasts to 5% to 25% in the bone marrow aspirate. Bone marrow must have adequate cellularity (e.g., > 15%) to determine response. PR status will not be included in calculation of response to the regimen. A repeat bone marrow aspiration after several weeks may be required to distinguish between a PR and increased blasts caused by bone marrow regeneration. A value of < 5% blasts may also be considered a PR if Auer rods are present.

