4.2.2 Concomitant Medications

4.2.2.1 Corticosteroids: Patients must be off steroids (unless physiologic replacement dosing) for at least 7 days prior to enrollment. If used to modify **immune adverse events** related to prior therapy, \geq 14 days must have elapsed since last dose of corticosteroid (See [Section 4.1.7.1.d](#)).

4.2.2.2 Investigational Drugs: Patients who are currently receiving another investigational drug are not eligible.

4.2.2.3 Anti-cancer Agents: Patients who are currently receiving other anti-cancer agents are not eligible [except hydroxyurea, which may be continued until 24 hours prior to start of protocol therapy].

4.2.2.4 Anti-GVHD agents post-transplant:

Patients who are receiving cyclosporine, tacrolimus or other agents to treat graft-versus-host disease post bone marrow transplant are not eligible for this trial.

4.2.3 Study Specific:

4.2.3.1 Patient has French-American-British classification (FAB) type M3 leukemia (acute promyelocytic leukemia) or identification of t(15;17).

4.2.3.2 Patient has isolated CNS involvement or isolated extramedullary relapse.

THIS PROTOCOL IS FOR RESEARCH PURPOSES ONLY, SEE PAGE 1 FOR USAGE POLICY

4.2.3.3 Patient with known HIV infection are eligible if he or she has a negative HIV serology and an undetectable viral load.

4.2.3.4 Patient known to have one of the following concomitant genetic syndromes: Bloom syndrome, ataxia-telangiectasia, Fanconi anemia, Kostmann syndrome, Shwachman syndrome or any other known bone marrow failure syndrome. Patients with Down syndrome ARE eligible for the study.

4.2.3.5 Patients must not weigh < 17 kg.

4.2.3.6 Patients must not have received prior therapy with a CD123 directed antibody or CD123 directed CAR T cells.

4.2.4 Infection: Patients who have an uncontrolled infection are not eligible.

4.2.5 Patients who have received a prior solid organ transplantation are not eligible.

4.2.6 Patients who in the opinion of the investigator may not be able to comply with the safety monitoring requirements of the study are not eligible.

4.2.7 Known hypersensitivity to murine, yeast, or recombinant proteins; polysorbate 80; recombinant human serum albumin; benzyl alcohol; or any excipient contained in the flotetuzumab drug formulation. Additionally, those patients who have had a hypersensitivity reaction to etoposide that is considered likely related to polysorbate 80 are not eligible.

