5.2 Criteria for Starting Subsequent Cycles

A cycle may be repeated every 29 days, with an optional ≤ 3 day respite period between each cycle. The optional ≤ 3 day respite period will be up to the treating physician's discretion. If a patient has progressive disease at any time point or is unable to achieve a PR following Cycle 2, subsequent protocol therapy must be discontinued. Due to a risk for disease rebound and recurrent CRS, patients are allowed to proceed to subsequent cycles while awaiting disease evaluation at the discretion of the treating physician. For patients with no evidence of disease after Cycle 1, subsequent cycles should be interrupted until ANC ≥ 500 μ L and platelets $\geq 20,000/\text{mm}^3$. Patients with persistent disease are permitted to continue flotetuzumab regardless of ANC and platelet counts. Laboratory parameters as defined in the eligibility section, [Section 4.0](#), must be met, and the patient must be eligible to continue agent administration per the requirements in [Section 6.0](#).

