8.0 EVALUATIONS/MATERIAL AND DATA TO BE ACCESSIONED

8.1 Required Clinical, Laboratory and Disease Evaluation

All clinical and laboratory studies to determine eligibility must be performed within 7 days

THIS PROTOCOL IS FOR RESEARCH PURPOSES ONLY, SEE PAGE 1 FOR USAGE POLICY

prior to enrollment unless otherwise indicated. Laboratory values used to assess eligibility (see [Section 4.0](#)) must be no older than seven (7) days at the start of therapy. Laboratory tests need **not** be repeated if therapy starts **within** seven (7) days of obtaining labs to assess eligibility. If a post-enrollment lab value is outside the limits of eligibility, or laboratory values are older than 7 days, then the following laboratory evaluations must be re-checked within 48 hours prior to initiating therapy: CBC with differential, bilirubin, ALT (SGPT) and serum creatinine. If the recheck is outside the limits of eligibility, the patient may not receive protocol therapy and will be considered off protocol therapy. Imaging studies, bone marrow aspirate, and biopsy must be obtained within 14 days prior to start of protocol therapy (repeat the imaging if necessary).

STUDIES TO BE OBTAINED	Pre-Study	During Cycle 1	Prior to Subsequent Cycles [^]
History	X	Weekly	X
Physical exam with vital signs	X	Weekly	X
Height, weight, BSA	X		X
Performance status	X		
CBC, differential, platelets	X	Twice Weekly (every 3 to 4 days) ³	Weekly ⁴
Pharmacokinetics		X ¹	X ¹
Anti-drug antibody (ADA)		X ¹⁰	X ¹⁰
Urinalysis	X		
Electrolytes including Ca ⁺⁺	X	Twice weekly (every 3 to 4 days) during Week 1, then weekly	X
Creatinine, ALT, bilirubin, AST	X	Weekly	X
Albumin	X		X
Imaging (CT or MRI) of chloroma (if clinically indicated)	X	End of Cycle 1 (if present at baseline)	End of each cycle (if present on previous study)
Bone marrow aspiration	X ^{5, 6, 12, 13}	End of Cycle 1 ⁵	End of every cycle
Pregnancy test ²	X		
ECHO or gated radionuclide study	X		X
EKG	X		X
Neurologic exam	X		X
Next-generation sequencing (NGS) MRD analysis	With bone marrow evaluation ^{7,13}	With bone marrow evaluation ⁷	With bone marrow evaluation ⁷
Peripheral T cell quantification		X ⁸	X ⁸
Cytokine analysis		X ⁹	X ⁹
Tumor Microenvironment Profiling	X ^{11, 13}		
Flow cytometry with minimal residual disease determination (MRD) ¹⁴		With bone marrow evaluation	With bone marrow evaluation

[^] Studies may be obtained within 72 hours prior to the start of the subsequent cycle.

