12.2.5 Progressive Disease (PD)

Increase in the absolute number of circulating (in peripheral blood) or bone marrow blasts of at least 50% from nadir or development of extramedullary disease.

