12.2.6 Stable Disease (SD)

Criteria for CR, CRp, CRI, CRc, PR, or progressive disease (PD) not met.

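### With an existing chloroma, the response categories can rank a cleared marrow (SD) below a partly cleared one (PR), because Section 12.2 has no rule for change in a lesion already present

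*Combined protocol and SAP*

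**What the plan says.** **Who can enrol.** The relevant exclusion, 4.2.3.2, is "Patient has isolated CNS involvement or isolated extramedullary relapse". Section 4.1.4 requires at least an M2 marrow, and requires radiographic clearance only where there is a history of CNS chloroma. A child with marrow disease plus a non-CNS chloroma is therefore eligible.

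**What is measured.** The evaluation table in Section 8.1 has a row for "Imaging (CT or MRI) of chloroma (if clinically indicated"). It applies before study, at the end of Cycle 1 if a lesion was present at baseline, and at the end of each later cycle if one was present on the previous scan.

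**How response is classified.**
- CR, CRp and CRi (12.2.1 to 12.2.3) each need a marrow below 5% blasts and no extramedullary disease or circulating blasts. Section 12.2.1 tolerates rare blood blasts during regeneration.
- PR (12.2.4) is "A decrease of at least 50% in the percentage of blasts to 5% to 25% in the bone marrow aspirate", with two further marrow provisions: "Bone marrow must have adequate cellularity (e.g., > 15%) to determine response" and "A value of < 5% blasts may also be considered a PR if Auer rods are present". The same section says that PR does not enter the response calculation.
- PD (12.2.5) is an increase in circulating "or bone marrow blasts of at least 50% from nadir or development of extramedullary disease".
- SD (12.2.6) is the remainder: "Criteria for CR, CRp, CRI, CRc, PR, or progressive disease (PD) not met". CRc is named there but not defined in Section 12.2.

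**What depends on the categories.** Under Section 5.2, if a patient has progressive disease or "is unable to achieve a PR following Cycle 2, subsequent protocol therapy must be discontinued". Sections 5.1 and 10.1(b) also make continuation depend on at least a PR after two cycles. Section 10.1(a) lists clinical or radiographic progression as a reason for removal and refers to Section 12 for its meaning.

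**The concern.** An ordered response scale should not place a patient with less disease below one with more. Here PR has a floor of 5% marrow blasts, and the categories meant for marrows under that floor are closed to anyone with residual extramedullary disease. A patient who clears the marrow while a known chloroma shrinks but remains falls through to SD. In the other direction, growth of a known chloroma enters neither PR nor PD. PR has no extramedullary condition, and the 50%-from-nadir limb of PD covers only blood and marrow blasts.

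Two things are at stake. One is the descriptive PR/SD/PD distribution that serves aim 1.2.2. The other is the continuation decision after Cycle 2, which is tied to the same labels.

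**Working it through.** The plan states no figure to reproduce. The check applies 12.2.1 to 12.2.6 literally: PD first, then CR/CRp/CRi, then PR, with SD as the remainder.

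**Inputs.** The definitions are those in Section 12.2. The marrow values are illustrative assumptions: baseline 60% blasts, adequate cellularity, no circulating blasts, recovered counts.

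**Percentage falls.**
- 60% to 20%: (60 − 20)/60 = 67%, and 20% lies within 5% to 25%, so the PR condition is met.
- 60% to 2%: (60 − 2)/60 = 97%, but 2% lies below the band, so PR is not met unless Auer rods are present.

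**Classification.**

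| Marrow | Chloroma | Category |
|---|---|---|
| 60% to 20% | present at baseline, growing | PR |
| 60% to 2%, no Auer rods | present at baseline, shrinking, still there | SD |
| 60% to 2%, Auer rods | as above | may be PR |
| 60% to 20% | new | PD |
| 60% to 2% | none | CR |

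**Ordering with a persisting chloroma, no Auer rods.** Final marrow blasts of 2% give SD; 10%, 20% and 25% give PR; 26%, 40% and 60% give SD. The category rises and then falls again as the marrow improves. Without a chloroma, 2% gives CR and the order is monotone.

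**Circulating blasts.** A marrow below 5% with genuinely persistent blood blasts, not up 50% from nadir, is barred from CR/CRp/CRi and misses the PR band, so it is SD. A marrow of 20% with the same blood finding is PR.

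**Does *development* include growth?** Section 12.2.7 pairs reappearance with development of extramedullary disease when defining relapse. That supports reading the word as appearance. No size threshold is given anywhere in Section 12.

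**How many patients.** The documents do not state how many children will have marrow plus extramedullary disease. Assume 5% to 15%. Section 11.1 gives up to 18 evaluable patients for dose finding and up to 6 more for PK, hence 18 to 24.
- With baseline extramedullary disease: 0.05 × 18 = 0.9 to 0.15 × 24 = 3.6.
- Both discordant patterns need a marrow response. As a rough guide, take the adult overall response rate in Section 2.3.1, printed as 26% with the count 6/27 (which is 22%). This gives 0.9 × 0.22 = 0.2 to 3.6 × 0.26 = 0.9 patients, before requiring that marrow and lesion disagree.
- The ceiling, if every such patient were discordant, is 3.6.
- One patient is 1/24 = 4.2 to 1/18 = 5.6 percentage points of the category listing.

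**The case against.** The case against is mainly about scope, and much of it stands.

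- A reader might infer that every patient with baseline extramedullary disease is misclassified. The documents do not support that. If the lesion clears with the marrow, or the marrow fails to respond or progresses, the patient is classified sensibly. Section 12.2.8 also sets aside aplastic or severely hypocellular marrows. And because 12.2 takes best response over up to four cycles, a patient scored PR at one evaluation who later clears the marrow keeps PR as best response.
- A reader might infer that the reported response rate is biased. It is not: PR is left out of the response calculation, neither discordant pattern is CR, CRp or CRi, and Section 11.5 makes the analysis descriptive.
- A reader might infer that a child with a growing chloroma would have to stay on treatment. Continuation after PR is permissive, 10.1(i) allows removal on the physician's judgement, and an assessor might invoke 10.1(a). But 10.1(a) defers to Section 12, which has no criterion for an existing lesion. These provisions also work in one direction only: none of them addresses the cleared marrow scored SD.
- Section 12.2 derives its criteria from cited international recommendations, which may say more. That cannot be checked here, and the text that sites will apply is the protocol's own.
- Chloroma imaging is conditional on clinical indication, so lesion change may not be recorded for every affected patient.

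None of these removes the inversion in the written definitions.

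**Conclusion.** The point holds as a defect in the response definitions. With the same residual extramedullary disease, a marrow of 5% to 25% can score PR while a marrow below 5% scores SD, and growth of a known lesion has no place in either PR or PD. The SD result rests on an evaluable marrow, no Auer rods and a lesion still present. The parallel result for circulating blasts needs true persistence beyond what 12.2.1 tolerates.

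The size is small: probably fewer than one patient to a few, on an assumed 5% to 15% prevalence that the documents neither give nor contradict. The inversion itself does not depend on that figure. The CR/CRp/CRi rate, DLT assessment, MTD and sample size are unaffected. What is affected is the descriptive PR/SD/PD distribution and the labels on which 5.1, 5.2 and 10.1(b) base continuation. It should be corrected, but the primary aims do not depend on it.

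**What to change.** Amend 12.2.4 to 12.2.6, for reporting, so that the ordering is coherent:

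1. State how change in a pre-existing extramedullary lesion enters PR and PD, and how that change is to be judged.
2. Name the category for a marrow below 5% that misses CR/CRp/CRi only because of residual extramedullary disease or circulating blasts. It should not rank below a marrow of 5% to 25% with the same residual disease.
3. Define CRc or delete it from 12.2.6.

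The sponsor must then reconcile the following with the amended definitions: 8.1 (imaging without a reading rule), 10.1(a) (radiographic progression that Section 12 does not define for an existing lesion), and 5.1, 5.2 and 10.1(b) (continuation by category). Which patients should stop or continue therapy is for the sponsor to settle; nothing is proposed on that here.

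The cost is a small wording change, possible reclassification of an occasional patient, and a need to image known lesions consistently, since the present schedule is conditional on clinical indication. No additional patients or marrow samples are needed.
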